- 1) Unable to provide informed consent, assessed with knowledge questions about the material presented during the informed consent process that individuals must correctly answer before providing consent to participate.  
*Rationale:* Participants must have a clear understanding of what is involved in the study prior to enrolling.
- 2) Report a history of an allergic reaction to varenicline.  
*Rationale:* Varenicline is a treatment component in both study arms.
- 3) Currently pregnant, planning to become pregnant, or breastfeeding.  
*Rationale:* There is limited information on the safety of varenicline in pregnant women.  
46,47

- 4) Past-month suicidal ideation with plan or intent, or past 12-month history of suicidal behaviors or attempts, based on the primary care screening version of the Columbia Suicide Severity Rating Scale (C-SSRS).  
*Rationale:* Due to past reports of suicidal ideation in patients taking varenicline and limited research on the safety of prescribing varenicline to individuals with recent suicidal ideation or behaviors, we do not believe it is appropriate for these patients to participate in the study.
- 5) Self-reported psychiatric hospitalization in the past 3 months.  
*Rationale:* Varenicline carries a caution label for neuropsychiatric events. There is also limited research on the use of varenicline in patients with unstable mental illness. Hence, we do not feel that it is appropriate to include patients with a recent psychiatric hospitalization in the study.

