## **V. STUDY PROCEDURES**

### A. Study visits and measurements

A complete timeline of study activities is depicted in Figure 3 below. In total, this study will involve a screening visit, an enrollment visit, a randomization and baseline clinician visit, 2 additional clinician visits, 5 tobacco coaching sessions, 10 on-treatment monitoring visits over 12 weeks, and a post-treatment outcome assessment visit at 24 weeks. Participants must complete their enrollment visit within 2 weeks of their screening visit. The randomization and baseline clinician visit must be completed within 4 weeks of enrollment. During this visit, participants will be encouraged to set a quit date for the following week. Participants who are prescribed varenicline by the clinician will attend 2 follow-up clinician visits at weeks 3 and 7 (+/- 1 week). The first tobacco coaching session will occur on participants' quit date and the remaining 4 sessions will coincide with on-treatment monitoring visits at 2, 4, 8 and 12 weeks (or within one week after each of these time points). On-treatment monitoring visits will begin 1 week after the quit date. Selected participants will additionally be asked to participate in qualitative interviews at the end of treatment (12 weeks) and at the end of follow-up (24 weeks). The content and measurements involved in each of these visits are described below.

**Figure 3.** Study activities timeline

Week:	Pre-Treatment			On-Treatment									Post Treatment	
	-2	-1	0	1	2	3	4	5	6	7	8	10	12	24
Screening	•													
Enrollment	•													
Baseline Survey	•													
Randomization		•												
Clinician Visit		•				•				•				
Quit Date			•											
Tobacco Coaching			•		•		•				•		•	
Monitoring Visit 				•	•	•	•	•	•	•	•	•	•	
Outcomes Assessment 														•
Follow-up Survey													•	
Interview												•	•	

Notes: 1) Includes a point of care saliva cotinine test and a brief questionnaire; 2) Includes a second non-point of care saliva cotinine test from J2 Laboratories

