Depending on space availability, participant preference, and the safety of having in-person interactions based on the status of the COVID-19 pandemic, study participants may complete surveys, coaching sessions, clinician visits, and qualitative interviews in the following ways: **A) On-site in-person:** Staff may administer the surveys/provide coaching in-person at a private area in the clinic space while adhering to physical distancing guidelines. **B) On-site virtual:** Study staff will set up a tablet in a separate on-site room for participants and administer the survey/provide coaching via Microsoft Teams or Enterprise Zoom. **C) Remote and virtual:** Participants with access to a phone, smartphone, or computer can complete the surveys, coaching sessions, clinician visits, and/or interviews virtually with study staff via phone call, Microsoft Teams, or Enterprise Zoom.

Regardless of how participants complete study visits, the PI, [name], and/or the study clinician will be available to advise study staff and speak with participants as needed. Any questions or concerns raised during the consent or enrollment phase in addition to any issues unrelated to varenicline raised throughout the study will be directed to the PI. Any questions or concerns related to varenicline raised throughout the study will be directed first to the study clinician, with the PI serving as back-up.

**1) Screening visit:** Participants will be screened for study eligibility through measurement of the specific data variables listed in section VI.A. Participants who are proactively contacted for recruitment or who contact study staff directly will be offered the option to complete the eligibility screener questions over the phone. If their responses to the questions suggest that they are eligible to participate, they will be invited to meet with study staff in person at JYP to confirm their eligibility with a saliva test for cotinine. If the cotinine saliva test is consistent with current smoking, participants will be able to proceed with enrollment procedures. Both the eligibility screener saliva test and all enrollment procedures need to occur within 2 weeks after the participant answered the eligibility screener questions. Eligible participants who complete all components of the eligibility screening in-person during open screening hours will be asked to come back at a later time to complete enrollment procedures (also within 2 weeks).

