**2) Enrollment visit:** The enrollment visit will occur within 2 weeks after completing the screening visit. If more than 2 weeks has elapsed since screening, participants will need to be rescreened before proceeding to enrollment. During the enrollment visit, eligible participants will provide written informed consent. Enrolled participants will then complete a baseline assessment that includes measurement of the specific data variables listed in section VI.A and a demographics/contact form that includes data variables listed in section VI.A. Participants will also be provided with their CT Payer cards (listed below in section XI.A) during this visit upon completion of the baseline assessment survey. Participants will receive \$25 for completing the

baseline survey. Prior to randomization visits, CRCs will look up enrolled participants in the BHCHP electronic health record (EHR) and will complete a chart review form (data variables to collect listed in section VI.A). Enrolled participants will then be randomized to a study arm in the manner described above.

**3) Randomization and baseline clinician visit:** The randomization and baseline clinician visit will occur within 4 weeks after completing the enrollment visit. If more than 4 weeks has passed since enrollment, participants will first need to undergo repeat screening to confirm their continued eligibility, followed by reassessment of baseline survey measures to inform randomization and identify conditions relevant to varenicline use (see below), before being allowed to proceed to randomization. During the randomization visit, study staff will reveal the participant's group assignment and set up the introductory video which will explain the study components and the study schedule. After the introductory video, staff will provide participants with a study cell phone if applicable (see section V.C.). The participant will then be seen by the study clinician, as described in more detail below. During this visit, participants will be encouraged to set a quit date for the following week. Participants will receive \$10 for attending this visit.

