varenicline at a maximum dose of 0.5 mg twice per day (half the maximum typical dose), which is the recommended dose for patients with severe renal impairment (eGFR < 30). Participants who agree to have labs drawn will be prescribed varenicline according to their eGFR results. If the participant's eGFR is <30, the clinician will prescribe varenicline at a maximum dose of 0.5 mg twice per day. If the participant's eGFR is ≥30, the clinician will up-titrate varenicline to the typical maximum dose of 1.0 mg twice per day. In all cases, study staff will send an Epic message to the PCPs of participants with any degree of CKD to inform them of their patient's enrollment in the study; however, the clinician will proceed with prescribing varenicline according to the above well-defined clinical protocols unless the PCP directly recommends otherwise.

- 3) **Higher-risk mental health states:** Participant suicidality will be assessed during the eligibility screener, and other mental health symptoms will be assessed during the baseline survey using multiple assessments, as described in section VI.A. If the participant reports vague suicidal ideation but is otherwise found to be at low risk of suicide based on the C-SSRS primary care screening instrument (patients with high risk will be excluded) or if the participant is considered moderate risk of suicide only due to suicidal behavior over 12 months ago, study staff will send the participant's PCP a direct message via Epic on the same day as the enrollment/baseline survey study visit informing them of their patient's enrollment in the study and requesting input regarding whether prescribing varenicline is appropriate. The same procedure will occur for participants with high scores on standardized mental health symptom instruments administered during the baseline survey (see Appendix 2). The study clinician will not prescribe varenicline to the patient until explicit permission from the PCP is granted.

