At the time of the baseline clinician visit, the participant may be undecided on whether they want to try varenicline, or final approval from the participant's PCP or other provider may still be pending. In these instances, the clinician can delay issuing a varenicline prescription for up to 2 weeks. Undecided participants will be told to inform study staff if they decide to take varenicline. If PCP/provider approval is still pending, the study clinician will directly contact the PCP/provider to ensure that a direct answer is provided within the 2-week window. Upon meeting with the participant, the study clinician may determine based on chart review or clinical assessment that the participant has concerning comorbidities, symptoms, or circumstances that were not uncovered during screening and enrollment. In these cases, the clinician may determine that direct PCP input is necessary before prescribing varenicline and will direct message the participant's PCP to obtain this input before prescribing.

For participants who are prescribed varenicline at baseline, treatment will continue for 12 weeks, distributed in 1-month allotments in conjunction with follow-up clinician visits at 3 and 7 weeks to assess medication adherence and tolerance. Dose adjustments will be made for participants who experience non-serious side effects.

The clinician will electronically send varenicline prescriptions directly to the BHCHP pharmacy or to an alternative pharmacy (based on patient request and current supply), where participants will be instructed to fill their prescriptions. The majority of participants will have MassHealth insurance and can obtain their prescription with a \$3.40 copay that can be waived by the pharmacy if needed. The BHCHP pharmacy is also a covered entity under the 340B low-cost medication program and can therefore dispense varenicline at a very low cost (~\$0.55 per month) to participants without insurance. Given the low cost of varenicline under 340B pricing

and the low likelihood of recruiting participants without MassHealth, BHCHP has agreed to voucher the medication costs for participants who have no insurance or who have insurance that only offers varenicline at a high copay. If a participant requests to use an alternative pharmacy, the clinician will electronically send the varenicline prescription to this preferred pharmacy instead.

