- Suicidal thoughts, intention, and behaviors since last study visit, as measured by a modified version of the C-SSRS (if applicable; every monitoring visit).
- Other adverse events not related to varenicline if reported by participant (every monitoring visit)
- All items italicized in the baseline survey table above at 12 weeks, or within 2 weeks post
- Saliva cotinine level from results of laboratory cotinine testing at 12 weeks, or within 2 weeks post

**4) Post-treatment outcome assessment visit data elements:** The following variables will be collected at 24 weeks, or within 2 weeks post, unless otherwise specified in parenthesis.

- Point-of-care saliva cotinine level (incentive participants only)
- Date and time last smoked all or most of a cigarette
- Date and time of last puff of a cigarette
- Number of smoking days in the past 7 days
- Number of quit attempts in the past 3 months
- Use of cessation aids
- Use of vape or e-cigarette in the past 7 days
- Use of other tobacco products in the past 7 days
- All items italicized in the baseline survey table above
- Laboratory saliva cotinine level

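### The suicidality, pregnancy and psychiatric-hospitalization exclusion items are listed only at screening, and no time limit runs from those answers to randomization, which can follow up to 42 days later without rescreening.

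*Combined protocol and SAP*

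**What the plan says.** Section III.A excludes people with "Past-month suicidal ideation with plan or intent, or past 12-month history of suicidal behaviors or attempts", people who are pregnant, planning pregnancy or breastfeeding, and people with a psychiatric hospitalization in the previous 3 months. Section VI.A.1 lists the items for these criteria among the screening variables. They do not reappear in the enrollment list in VI.A.2. Section V.B confirms the split for mental health: "Participant suicidality will be assessed during the eligibility screener, and other mental health symptoms will be assessed during the baseline survey".

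Two windows follow. Section V.A states: "Participants must complete their enrollment visit within 2 weeks of their screening visit". Section V.A.1 counts this from the screener answers: when the questions are answered by phone, the saliva test and all enrollment procedures "need to occur within 2 weeks after the participant answered the eligibility screener questions". Section V.A.3 then states: "The randomization and baseline clinician visit will occur within 4 weeks after completing the enrollment visit". Beyond 2 weeks (V.A.2) or 4 weeks (V.A.3) the person must be screened again; under V.A.3 the stated purpose is to check that the person still qualifies.

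At the randomization visit, V.A.3 has staff reveal the assignment, show the video and hand over a phone if needed. The clinician sees the participant after that. If the participant is undecided about varenicline, or the primary care provider (PCP) has not yet replied, Section V.B adds: "In these instances, the clinician can delay issuing a varenicline prescription for up to 2 weeks".

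**The concern.** An exclusion with a look-back period protects people only if the question is asked close to the point at which it matters. The protocol accepts this: it rescreens when a window lapses, and Section V.H makes participants who restart after the varenicline pause repeat the screener. Each clock, however, covers one leg of the journey, and none covers the whole distance from the screener answers to randomization.

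Section III.A says it is not appropriate for people with recent suicidality or a recent psychiatric hospitalization to take part, and it excludes pregnancy because safety information on varenicline is limited. Someone who comes to meet one of these criteria after screening, but stays inside both windows, can be randomized without being asked again on any listed form. What is at stake is whether the people randomized meet the protocol's own criteria on the day of randomization.

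**Working it through.** The plan gives no figure for the time from screener to randomization, so there is none to reproduce. The maximum follows from its windows.

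**Inputs**
- Screener answers to enrollment: at most 14 days (V.A, V.A.1, V.A.2).
- Enrollment to randomization: at most 28 days (V.A.3).
- Clinician visit to a delayed prescription: at most 14 days, only for participants who are undecided or awaiting a PCP reply (V.A.4, V.B).
- Look-back periods (III.A): one month, 3 months and 12 months, taken here as 30, 91 and 365 days. Pregnancy is a current status or plan and has no look-back.

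**Step 1: longest gaps**
- To randomization: 14 + 28 = 42 days (6 weeks).
- To a delayed prescription: 42 + 14 = 56 days (8 weeks).

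**Step 2: share of each look-back period, counted back from the later date, that falls after the screener**

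Share = min(1, gap / look-back).

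| Criterion | About 7 days (Figure 3) | 42 days | 56 days |
|---|---|---|---|
| Ideation, 30 days | 7/30 = 23% | 100% | 100% |
| Hospitalization, 91 days | 7/91 = 8% | 42/91 = 46% | 56/91 = 62% |
| Suicidal behavior, 365 days | 7/365 = 2% | 42/365 = 12% | 56/365 = 15% |

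With a 28-day month the first entry is 7/28 = 25% and the other two stay at 100%.

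**Step 3: the rescreening rule applied to two people, screener on day 0**
- Enrolled day 1, randomized day 30: 30 - 1 = 29 days, which exceeds 28. Rescreened.
- Enrolled day 14, randomized day 42: 14 days and 42 - 14 = 28 days, neither beyond its limit. Not rescreened, although the answers are 42 - 30 = 12 days older.

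The rule therefore does not order people by the age of their answers.

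**Step 4: the next scheduled C-SSRS**

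The quit date is set for about a week after randomization and the first monitoring visit is a week after that. This can be 42 + 7 + 7 = 56 days after the screener. The item there is "Suicidal thoughts, intention, and behaviors since last study visit, as measured by a modified version of the C-SSRS", and Sections VII.B and IX.F tie it to participants on study varenicline. It reaches back to the preceding visit, so no scheduled C-SSRS covers the interval between the screener and that visit.

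**Step 5: the other checks before drug**
- The baseline survey's mental-health instruments are given at enrollment, so they can be 28 days old at randomization.
- The chart review precedes the randomization visit (V.A.2). Its variables are not itemized under that name in VI.A.
- The clinician's history and assessment (V.A.4, V.B) take place on the day, after the arm is revealed, and decide whether and how to prescribe.

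None of these is described as re-applying the exclusions, and none mentions pregnancy.

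**The case against.** The strongest reply is that drug exposure does not rest on the screener. High scores on the baseline mental-health instruments block a prescription until the PCP gives explicit permission. Every PCP is told of the enrollment and can advise against varenicline. The clinician judges on the day whether a prescription is appropriate, and may seek PCP input on anything missed earlier (IV.A, V.A.4, V.B). This stands. A reader might infer that these conditions are never looked for after screening, or that people are prescribed varenicline on 8-week-old answers alone; the documents support neither.

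The size is also limited. Six and eight weeks are outer limits, Figure 3 shows about 1 week, and nothing shows how many participants would come near the limits. Eight weeks applies only to undecided or PCP-pending participants, and for those whose PCP must give permission the delay is itself a safeguard. At 42 days the screener still covers over half of the hospitalization window and nearly 90% of the 12-month behavior window. All of this stands.

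A reader might also infer damage to the intention-to-treat comparison, since Section VI.C counts a missing sample as non-abstinent. The documents do not support that. Varenicline is offered, not required; no section says that a person found unsuitable for it leaves the trial; and both arms share the same screening, windows and drug offer.

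The reply does not reach eligibility. The later checks govern prescribing, and the anomaly in the rescreening rule remains whatever the clinician does.

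**Conclusion.** The point holds as a gap in how eligibility is confirmed. The formal exclusion items are listed only at screening, the windows allow 42 days to randomization without rescreening, and at that limit the past-month ideation criterion is wholly unasked for the month before randomization, as is about 46% of the 3-month hospitalization window. For pregnancy the gap is a status that may change with no listed re-check. The rescreening rule is inconsistent with its own purpose because it counts from enrollment and not from the answers.

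This is a cheap improvement worth making. It is not evidence of unsafe prescribing or of bias between arms. It assumes the month lengths given above and that VI.A lists all the items asked. The prescribing algorithm (Appendix 2) and the C-SSRS forms (Appendix 3) are cited but were not in the text available; if either repeats these items before randomization, the gap narrows and the main text should say so.

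**What to change.** In Section V.A.3, state that the exclusions must still hold at randomization, and do one of two things:
- re-confirm the existing exclusion items, on the existing screener forms, before the arm is revealed; or
- count the rescreening window from the date of the screener answers instead of from enrollment.

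List the re-check in Section VI.A. The first option costs a few minutes at a visit that is already scheduled and paid. A few enrolled people will be found ineligible, but before randomization.

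Separately, reconcile Sections III.A, V.A.2 to V.A.4, V.B and VI.A on which answers govern contact with the PCP and a delayed prescription. PCP messages for flagged mental states now go out on the day of enrollment, which leaves up to 4 weeks for a reply before the clinician visit, so any change there has a cost in time. That clinical rule is for the sponsor to set.

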## **B. Drugs**

Participants in both study arms will be offered a prescription for varenicline, an FDA-approved, first-line smoking cessation medication that has been shown to be safe and effective in at-risk populations, including those with comorbid psychiatric conditions, alcohol use disorder and substance use disorders. In general, varenicline prescriptions will be issued by the study clinician who will meet with participants at the randomization visit to assess their health history and relevant comorbid conditions. In most cases, participants will receive a 1-month prescription for varenicline from the study clinician according to the recommended 7-day loading procedure of 0.5 mg daily on days 1-3 then 0.5 mg twice daily on days 4-7 before reaching the target dose of 1 mg twice daily on day 8.

After the completion of the enrollment visit, study staff will contact the participant's PCP to inform them of their patient's enrollment in a stop smoking study in which varenicline will be offered. Unless the participant reports a history of specific comorbidities, PCP permission will not be required before the study clinician meets with the participant and prescribes varenicline at the typical dosage. However, PCPs will be invited to respond to study staff messages to express any questions or concerns, and if the PCP recommends that varenicline is not prescribed, the study clinician will follow this recommendation. For participants with selected comorbidities, including seizure history, chronic kidney disease, or higher-risk mental states, we will follow a systematic algorithm to ensure safe varenicline prescribing (Appendix 2). Comorbidities will be assessed in various ways, including a) participants' responses to the eligibility screener and baseline survey items related to chronic medical conditions and mental health symptoms, b) review of documented comorbidities within participants' EHR, and c) baseline clinical assessment by the study clinician. The action plans in response to specific comorbidities (as visualized in Appendix 2) are explained further below:

- 1) **Seizures:** During the baseline survey, participants will be asked if they have a lifetime history of seizures, and if yes, whether they had a seizure in the past year. If the participant has had a seizure within the past year, study staff will send the participant's PCP a direct message via Epic on the same day as the enrollment visit informing them of their patient's enrollment in the study and requesting input from the PCP regarding whether a prescription for varenicline is appropriate. The study clinician will not prescribe varenicline to such a participant until explicit permission from the PCP is granted. If the participant has not had a seizure within the past year, study staff will still send the participant's PCP a direct message informing them of their patient's enrollment in the study and invite their input if they have any questions or concerns; however, the clinician will proceed with prescribing varenicline unless the PCP directly expresses that the participant should not take varenicline.
- 2) **Chronic kidney disease (CKD):** For participants with a history of CKD, our varenicline prescribing protocols are based on past research on varenicline use in patients with renal impairments and the recommendations listed on the Pfizer varenicline packet insert. During the baseline survey, participants will be asked if they have a lifetime history of CKD, and if yes, whether they are currently on dialysis. For participants on dialysis, the clinician will prescribe varenicline at a maximum dose of 0.5 mg once daily (a quarter of the typical maximum dose). For participants who are not on dialysis, the clinician will recommend that the participant completes lab testing to ascertain current serum eGFR levels. If the participant refuses new labs, the clinician will prescribe

varenicline at a maximum dose of 0.5 mg twice per day (half the maximum typical dose), which is the recommended dose for patients with severe renal impairment (eGFR < 30). Participants who agree to have labs drawn will be prescribed varenicline according to their eGFR results. If the participant's eGFR is <30, the clinician will prescribe varenicline at a maximum dose of 0.5 mg twice per day. If the participant's eGFR is ≥30, the clinician will up-titrate varenicline to the typical maximum dose of 1.0 mg twice per day. In all cases, study staff will send an Epic message to the PCPs of participants with any degree of CKD to inform them of their patient's enrollment in the study; however, the clinician will proceed with prescribing varenicline according to the above well-defined clinical protocols unless the PCP directly recommends otherwise.

- 3) **Higher-risk mental health states:** Participant suicidality will be assessed during the eligibility screener, and other mental health symptoms will be assessed during the baseline survey using multiple assessments, as described in section VI.A. If the participant reports vague suicidal ideation but is otherwise found to be at low risk of suicide based on the C-SSRS primary care screening instrument (patients with high risk will be excluded) or if the participant is considered moderate risk of suicide only due to suicidal behavior over 12 months ago, study staff will send the participant's PCP a direct message via Epic on the same day as the enrollment/baseline survey study visit informing them of their patient's enrollment in the study and requesting input regarding whether prescribing varenicline is appropriate. The same procedure will occur for participants with high scores on standardized mental health symptom instruments administered during the baseline survey (see Appendix 2). The study clinician will not prescribe varenicline to the patient until explicit permission from the PCP is granted.

At the time of the baseline clinician visit, the participant may be undecided on whether they want to try varenicline, or final approval from the participant's PCP or other provider may still be pending. In these instances, the clinician can delay issuing a varenicline prescription for up to 2 weeks. Undecided participants will be told to inform study staff if they decide to take varenicline. If PCP/provider approval is still pending, the study clinician will directly contact the PCP/provider to ensure that a direct answer is provided within the 2-week window. Upon meeting with the participant, the study clinician may determine based on chart review or clinical assessment that the participant has concerning comorbidities, symptoms, or circumstances that were not uncovered during screening and enrollment. In these cases, the clinician may determine that direct PCP input is necessary before prescribing varenicline and will direct message the participant's PCP to obtain this input before prescribing.

For participants who are prescribed varenicline at baseline, treatment will continue for 12 weeks, distributed in 1-month allotments in conjunction with follow-up clinician visits at 3 and 7 weeks to assess medication adherence and tolerance. Dose adjustments will be made for participants who experience non-serious side effects.

The clinician will electronically send varenicline prescriptions directly to the BHCHP pharmacy or to an alternative pharmacy (based on patient request and current supply), where participants will be instructed to fill their prescriptions. The majority of participants will have MassHealth insurance and can obtain their prescription with a \$3.40 copay that can be waived by the pharmacy if needed. The BHCHP pharmacy is also a covered entity under the 340B low-cost medication program and can therefore dispense varenicline at a very low cost (~\$0.55 per month) to participants without insurance. Given the low cost of varenicline under 340B pricing

and the low likelihood of recruiting participants without MassHealth, BHCHP has agreed to voucher the medication costs for participants who have no insurance or who have insurance that only offers varenicline at a high copay. If a participant requests to use an alternative pharmacy, the clinician will electronically send the varenicline prescription to this preferred pharmacy instead.

